* When appropriate, subjects will be provided with the following additional pertinent information after participation (if you have no plans to provide additional information to subjects please provide justification):

Individuals who are prescreened will be provided with information about the study including contact information for study personnel. If these individuals contact study personnel to express interest in participation, they will be provided with additional pertinent information about the study during the screening process (see Screening Script).

View: 9.3 Waiver of Documentation of Informed Consent

Waiver of Documentation of Informed Consent

You have selected a waiver of Documentation of Informed Consent

1.0

This is a request for Waiver of Documentation of Informed Consent because this research study conforms to either A and/or B (Check if 'yes' and provide the verifying information requested):

* A: The only record linking the subject and the research would be the consent document and the principal risk would be potential harm resulting from a breach of confidentiality. Each subject will be asked whether the subject wants documentation linking the subject with the research, and the subject's wishes will govern. Yes No

AND/OR

* B: The proposed study poses minimal risk to the subjects. Yes No

If yes, please explain why the proposed study poses minimal risks to the subjects. (Outline the subject's involvement in the project and why the study poses minimal risk) :

If yes, please explain why the proposed study poses minimal risks to the subjects. (Outline the subject's involvement in the project and why the study poses minimal risk) :

A Waiver of Documentation of Informed Consent is requested for the telephone screening procedure and initial Consent and Screening appointment only. Eligible participants will be asked to provide written informed consent during their first in-person study visit. During the screening procedures conducted by phone or video call, potentially eligible participants will be asked to answer questions necessary to evaluate study eligibility. They will be informed that they are not required to answer any questions they

do not wish to. Potentially eligible participants will also have the option of providing verbal consent for study personnel to access their medical record in order to confirm eligibility. Screening data will be maintained in a secured location for eligible participants. Data from ineligible participants, as well as those who do not subsequently provide written informed consent, will also be maintained in a secured location. In lieu of written consent at the time of the remotely conducted Consent and Screening visit, when applicable, the investigator will send a written consent form by mail. Participants who are determined through remote screening to be eligible and willing to enroll in the study will bring their signed consent form to the baseline appointment (the first in-person encounter) or will return the signed form by mail. If the signed form has not been received by the time of the initial in-person visit (either by mail or personal delivery by the participant), the participant will be asked to sign a new copy of the consent form before any in-person research procedures commence. In this way, written informed consent will be documented by/at the time of the first in-person study visit.

2.0 * The research involves no procedures for which written consent is normally required outside of the research context. Research procedures include:

- 1.) Potentially eligible participants will be asked to listen to information about the study.
- 2.) Potentially eligible participants will be asked to consent to study personnel accessing their medical record in order to evaluate eligibility. They will have the option to decline.
- 3.) Potentially eligible participants will be asked to answer a series of questions in order to determine eligibility to participate in the study. Questions will focus on health and substance use history, as well as basic demographic data. They will have the option to decline to answer any question they do not wish to.
- 4.) Eligible participants will be asked to provide contact information and to schedule a study visit if they are interested in participating.
- 5.) Participants may also be asked to answer questions in the context of interview, cognitive screener, and/or self-report measures.

3.0 * Explain how whenever appropriate, the subjects will be provided with additional pertinent information (e.g. an information sheet):

Participants will provide written consent and will be provided with a copy of the signed study consent form, upon presentation at the first in-person study visit.

4.0

Please upload SCRIPT here:

Document Description Version Number

View Screening Script - Phone & In-Person Versions(0.06) 0.06

ID: Pro00002689

View: 9.4 Consent Forms & Process of Consent

Consent Forms & Process of Consent

1.0 Upload the completed forms into the correct lists below.

1.1

Informed Consent Form (clean copy):

Document Modified Date Version Number

[View Goldstein Substudy Consent\(0.03\) 2/11/2021 12:00 AM 0.03](#)

[View Patient Consent\(0.08\) 11/16/2020 12:00 AM 0.08](#)

[View Telehealth Substudy Consent\(0.03\) 11/4/2020 12:00 AM 0.03](#)

1.2

Provider Behavior Informed Consent Form (clean copy):

Document Modified Date Version Number

There are no items to display

1.3

Screening Informed Consent Form (clean copy):

Document Modified Date Version Number

[View Screening Consent\(0.08\) 11/16/2020 12:00 AM 0.08](#)

2.0

Consent Forms (modified copy):

Document Modified Date Version Number

[View Goldstein Substudy Consent Tracked Changes\(0.01\) 2/12/2021 9:45 AM 0.01](#)

View Patient Consent - Tracked Changes(0.04) 8/27/2019 1:16 PM 0.04

View Screening Consent - Tracked Changes(0.06) 10/9/2020 1:10 PM 0.06

A Healthy Comparison Subject Consent has now been added.

3.0 * Describe how, where, when, and by whom the consent process will be initiated:

The consent document(s) will be thoroughly and extensively reviewed with participants and we will allow sufficient time to make an informed, voluntary decision. For those adults who wish to involve a family member or friend in the consent process, we will arrange to do so. We will make it clear that the Veteran's decision to participate or not will have no effect on their treatment or relationship with the VA Healthcare System.

For the majority of participants, an initial eligibility screening will be conducted by telephone and written consent will not be provided at this time. (A Waiver of Documentation of Informed Consent has been requested to cover telephone screening procedures). However, it is possible that interested patients may also prefer to participate in the initial eligibility screening in person and, in such cases, a separate Screening Consent will be used to document written consent for initial screening procedures only and will also include HIPAA authorization . This document covers all information conveyed through the telephone screening script and will be thoroughly and extensively reviewed with all individuals who participate in in person eligibility screening. In person eligibility screening procedures will be conducted in a private interview room or office at the Research Office Building (Building 30) or a private office at Building 29.

Interested participants who are eligible on the basis of initial eligibility screening (either by phone or in person) will be scheduled for a separate appointment with a member of the research team, during which the informed consent document for the full protocol will be extensively reviewed for comprehension and witnessed oral and written consent to participate will be obtained. Potential risks and benefits from this research will be reviewed. This appointment will typically be conducted in a private interview room or office at the Research Office Building (Building 30) or a private office at Building 29. However, it is also possible that this appointment will be conducted remotely if judged to be in the best interest of the Veteran. In such cases, written consent will then be obtained at the time of the first in-person visit for those who are eligible to continue on to baseline assessment and randomization. Participants will be provided with a copy of their signed consent form at that time.

Participants may be asked to consent to optional activity and heartrate monitoring (i.e., Goldstein Substudy 2) after they have been assigned to one of the two Contingency Management treatment conditions.

4.0

* Will you be maintaining a Master List of Subjects?

Yes

5.0 * Describe when the subject's name will be added to the master list and how the list will be maintained in a secure fashion.

A record of all participants screened for participation in this study will be maintained in our secure Dacima database; identifiable information will only be accessible to those with a need to view this information. Participants who have provided written, informed consent to participate in the full study protocol will be added to a secure master list, maintained in Dacima. All data will be retained in accordance with the Records Control Schedule.

View: 10.0.0 Data Security and Privacy: Data Types Storing

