Power Analysis and Sample Size. In analyses of baseline predictors of treatment response in CM recipients (estimated $n = 119$ -140) and long-term (i.e., six month) outcomes (estimated $n = 105$ -140), using the statistical rule of thumb of needing 10 observation per predictor, our originally projected sample size would provide adequate power to include 10-14 variables in regression-based analyses. Random Forest methods are further supported for an expanded set of variables, as this highly flexible and powerful approach has been validated in “wide datasets,” wherein the number of predictors exceeds the number of observations. With the anticipated enrollment of 140 participants, there will additionally be adequate power ($\beta = 0.20$, alpha = 0.05) to detect an effect size of $f = 0.12$ for the treatment adherence (adherent, non-adherent) X time (baseline, follow-up) interaction, supporting planned comparison of treatment-related change in neural and cognitive-behavioral measures between PBCM adherent and non-adherent Veterans. Assuming 15% attrition, the estimate of the detectable effect size for the treatment X time interaction for a total sample size of 119 is $f = 0.13$. The anticipated effect size of treatment-related change in synchronization likelihood between ACC-IPFC electrode sites is not known. However, previous work has established a medium-to-large effect size for treatment-related change in the ERN and N2 (in association with cognitive training).[74,75]

It was necessary to revise our original analytic plan to accommodate a smaller sample size than that originally projected. Recruitment under the current protocol was initially delayed due to institutional barriers that prevented timely acquisition of our EEG system. While recruitment was promptly initiated after our equipment was finally received, approximately three months later, all research activities were suspended due to risks posed by the COVID-19 pandemic. Due to the collection of EEG data and the nature of the interventions under study (e.g., need to be in the physical presence of the prize cabinet to potentially benefit from the increased psychological proximity of reward), it was not possible to convert the current protocol to be conducted fully remotely during the pandemic. A series of administrative

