To address limitations related to the ratio of observations to predictors in the context of our reduced sample size, we revised our predictive analytic approach (Specific Aim 1) to prioritize model stability and interpretability, while framing results as more preliminary in nature. With respect to Aim 1, a revised sample size of ~50 participants was identified as sufficient to support investigation of up to five candidate predictors: e.g., two EEG-derived metrics, one clinical measure, one neurocognitive measure, and treatment condition. Recent simulation-based work (Austin & Steyerberg, 2015) further suggests that as few as two participants per predictor may be adequate, supporting investigation of the original candidate set even within the reduced sample. Two consulting biostatisticians endorsed this revised approach and further recommended modeling repeated binary outcomes over the course of CM treatment to improve power. In line with this recommendation, we modeled 24 repeated binary outcomes per participant, yielding up to $24 \times n$ observations across n participants. However, recognizing that the effective number of independent events remains tied to the number of participants rather than the number of observations, we adopted a two-stage variable selection process to reduce the risk of overfitting. In the first stage, we screened predictors using single-predictor longitudinal logistic regression models, identifying those with theoretically plausible associations with the outcome. This process narrowed our total number of candidate predictors. In the second stage, we applied stepwise forward selection guided by the Akaike Information Criterion (AIC) to construct a parsimonious, interpretable multivariate model. To further assess model robustness and generalizability, we evaluated predictive performance using leave-one-out cross-validation (LOOCV).

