Implications of our reduced sample size were also considered for Specific Aim 2, which involves longitudinal analysis of change in key neurocognitive metrics with adherence and abstinence as potential covariates. Based on guidance from statistical consultants, a sensitivity analysis indicated that a total sample size of 36 participants with both pre- and post-treatment data would provide adequate power to detect small to medium effect sizes ($f = 0.17\text{--}0.30$). This revised projection reflects the practical constraints of the available sample while maintaining sufficient power for detecting meaningful change over time in the context of repeated measures analysis. As an alternative analytic strategy, a median split approach to adherence and abstinence may be considered if data suggest that dichotomization would enhance interpretability or improve model stability in the context of limited sample size. While treating these variables as continuous covariates is generally preferred due to increased power and retention of variance, a binary approach may be appropriate in cases of non-linear relationships, bimodal distributions, or when simplifying the model structure offers clear interpretive advantages.

Specific Aim 1. Evaluate the utility of EEG and cognitive-behavioral measures of FMDM as predictors of differential treatment outcomes in TangiblePBCM versus VoucherPBCM. A significant interaction between CM treatment condition (i.e., TangiblePBCM versus VoucherPBCM) and neurocognitive indices

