*** Please provide a justification for the sample size:**

Power Analysis and Sample Size. In analyses of baseline predictors of treatment response in CM recipients (estimated n = 119-140) and long-term (i.e., six month) outcomes (estimated n = 105-140),

using the statistical rule of thumb of needing 10 observation per predictor, there will be adequate power to include 10-14 variables in regression-based analyses. Random Forest methods are further supported for an expanded set of variables, as this highly flexible and powerful approach has been validated in “wide datasets,” wherein the number of predictors exceeds the number of observations. With the anticipated enrollment of 140 participants, there will additionally be adequate power ($\beta = 0.20$, alpha = 0.05) to detect an effect size of $f = 0.12$ for the treatment adherence (adherent, non-adherent) X time (baseline, follow-up) interaction, supporting planned comparison of treatment-related change in neural and cognitive-behavioral measures between PBCM adherent and non-adherent subgroups. Assuming 15% attrition, the estimate of the detectable effect size for the treatment X time interaction for a total sample size of 119 is $f = 0.13$. The anticipated effect size of treatment-related change in synchronization likelihood between ACC-IPFC electrode sites is not known. However, previous work has established a medium-to-large effect size for treatment-related change in the ERN and N2 (in association with cognitive training) [69,70]. We have also proposed to compare the treatment-seeking CUD sample to the approximately 45 healthy controls who may be invited to participate in a comparison sample. Data from controls would help determine how CM-referred veterans differ from healthy individuals with respect to approaches to rewarding abstinence. However, it was ultimately not possible to enroll a sufficient healthy comparison sample at our site. In addition, due to factors that negatively impacted participant accrual over the course of the current study (as described elsewhere in the protocol) a revised analytic approach was developed to make use of a sample size that was significantly reduced relative to that originally projected.

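### Aim 1 is sized by a variable-count rule labelled as power: no detectable effect is given for the Hypothesis 1a interaction, and the revised count at about 50 has no room for its product terms

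*Combined protocol and SAP*

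**What the plan says.** Section 6, item 4.0 sizes Aim 1 "using the statistical rule of thumb of needing 10 observation per predictor". It applies this to 119 to 140 participants for treatment response and 105 to 140 for six-month outcomes, and concludes that "there will be adequate power to include 10-14 variables in regression-based analyses". The item ends by noting that a revised approach was developed for a much smaller sample, but it does not give the revised n.

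Section 4.1 (analysis plan) has the same paragraph with the tense changed: "our originally projected sample size would provide adequate power to include 10-14 variables in regression-based analyses". It then says that "a revised sample size of ~50 participants was identified as sufficient to support investigation of up to five candidate predictors". The example given is two EEG metrics, one clinical measure, one neurocognitive measure and treatment condition.

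Under Specific Aim 1, section 4.1 states Hypothesis 1a as an interaction: "A significant interaction between CM treatment condition (i.e., TangiblePBCM versus VoucherPBCM) and neurocognitive indices" of FMDM function. It names five FMDM measures (alpha suppression, ERN, parametric N2, Brown-Peterson score and the change in ln(k)), three example clinical indicators, and self-report scores. The revised model is a longitudinal logistic regression on 24 binary session outcomes per participant, with single-predictor screening followed by forward selection on AIC.

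**The concern.** Ten participants per predictor guards against overfitting. It does not say how large an effect the trial could detect. Aim 2 has a real power statement in the same paragraph (alpha, beta and a detectable f); Hypothesis 1a has none.

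The revised analysis also makes the count matter more. A regression tree can find an interaction without being told to look for it. A logistic regression tests one only if the product term is entered, and each product uses part of the allowance. A list of four markers or measures plus condition therefore does not cover the hypothesis it is meant to support.

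The treatment-matching rows of Table 1 (section 2, item 5.0) depend on this interaction. Without a stated detectable effect, a null Hypothesis 1a could be read as evidence that marker-guided choice between the two variants does not matter, when the sample could not have shown a moderate interaction reliably.

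**Working it through.** **1. The plan's own figure.** Capacity = n/10, with n from section 6, item 4.0 and section 4.1.
- 105/10 = 10.5; 119/10 = 11.9 (119 = 140 × 0.85); 140/10 = 14. This reproduces 10-14.
- Revised: 50/10 = 5. This reproduces the five candidates.

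No effect size, alpha or power enters either figure.

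**2. Counting the product terms, original size.** Assume one product with condition for each of the five named FMDM measures.
- FMDM only: 5 + 1 + 5 = 11 terms. Participants per term: 140/11 = 12.7; 119/11 = 10.8; 105/11 = 9.5.
- With the three named clinical indicators: 14 terms. 140/14 = 10.0; 119/14 = 8.5; 105/14 = 7.5.

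The FMDM model meets the rule at 119 and 140 and misses it only at 105.

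**3. Counting the product terms, revised size.** The example has 5 terms. Three of them are FMDM markers (two EEG, one neurocognitive). Adding their products gives 5 + 3 = 8 terms, and 50/8 = 6.25 participants per term. A model that keeps to 10 per term at 50 could hold condition, two markers and two products: 1 + 2 + 2 = 5.

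**4. Detectable interaction.** Assumptions: outcome as each person's success rate, one standardised moderator, equal arms, alpha 0.05, 80% power, and a noncentral F test with 1 and n − 4 df and noncentrality f2 × n. With equal arms, f2 = (slope difference)²/4, the slope difference being in residual SD.

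| n | detectable f2 | slope difference |
|---|---|---|
| 140 | 0.057 | 0.48 |
| 119 | 0.067 | 0.52 |
| 105 | 0.076 | 0.55 |
| 50 | 0.164 | 0.81 |

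At 50, equal and opposite slopes of ±0.405 correspond to correlations of 0.405/√(1 + 0.405²), about ±0.37. The detectable f2 is 0.164/0.057, about 2.9 times that at 140. Fitting 8 terms instead of 3 changes it only to 0.165.

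**5. Power over an assumed range.** The documents give no effect size for this interaction, so a range is shown.

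| f2 | n = 140 | n = 119 | n = 50 |
|---|---|---|---|
| 0.02 | 38% | 33% | 16% |
| 0.05 | 75% | 68% | 34% |
| 0.10 | 96% | 93% | 59% |
| 0.15 | >99% | 99% | 76% |

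**6. Do repeated sessions help?** Section 4.1 itself says that the effective number of events stays tied to participants. A simulation with 24 binary sessions each, 50% success, cluster-robust logistic regression and an interaction odds ratio of 2 per SD (assumed) gave these powers:
- n = 50: about 56% with a random-intercept SD of 1, and 23% with an SD of 2 (both assumed);
- n = 140: about 94% and 46%.

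**The case against.** The strongest reply has five parts.

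- **The plan claims no power for Aim 1 at about 50.** Section 4.1 confines the 10-14 statement to the original projection, explains the shortfall, and calls the revised results preliminary. This stands for section 4.1. Section 6, item 4.0 keeps the unqualified present-tense claim, and calling results preliminary does not say which effects a null result leaves open.
- **Section 4.1 also cites simulation work supporting two participants per predictor.** That would allow 50/2 = 25 terms, so 8 would fit. True as a count, but it is still not a statement of power for an interaction.
- **The list of five is only an example, and the revised plan selects stepwise.** Also true: the 8- and 11-term models are illustrations, not models the plan says it will fit all at once. But no product term is named anywhere in the revised approach.
- **The original methods were trees, random forests and arm-specific regressions, which need no product terms.** This stands for those methods. The disputed sentence concerns regression, and the revised method is regression.
- **The per-person rate is not the planned session-level outcome.** Correct. The detectable effect is an approximation, and the simulation in the working shows how far the answer depends on between-person variation.

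A reader might infer that the original sample was also inadequate. The documents do not support that. The 10-14 figure reproduces, the 11-term model fits at 119 to 140, and power there runs from 33-38% to 93-96% as f2 goes from 0.02 to 0.10. The miss at 105 concerns six-month outcomes, whereas Hypothesis 1a as worded in section 2, item 3.0 is about treatment response.

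**Conclusion.** The point holds in a limited form. Aim 1 rests on n/10, labelled as power in section 6, item 4.0, and no detectable effect is stated for the Hypothesis 1a interaction. That item is out of step with section 4.1: it keeps 10-14 variables in the present tense and omits the revised n, at which the same rule gives 5. The revised example spends all 5 before any product term; three FMDM products bring it to 8 terms at about 6 participants each.

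At about 50, 80% power requires f2 of about 0.16 (slope difference about 0.81 residual SD, or correlations of roughly ±0.37 if opposite in the two arms). This assumes one moderator, equal arms, alpha 0.05 and a per-person rate. A null result would be inconclusive for smaller interactions. It should not be described as uninformative for every effect, since power is 76% at f2 = 0.15. For the original projection, power is undemonstrated and not shown to be inadequate.

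**What to change.** **Section 6, item 4.0.** Limit the 10-14 statement to the originally projected sample, as section 4.1 already does. State the revised n. Describe the rule as a limit on model size and drop the word power.

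**Section 4.1, revised Aim 1 approach.**
- Name the few marker-by-condition products to be entered in the longitudinal logistic model.
- Count them in the predictor allowance. Under the plan's own rule of ten, about 50 participants allow roughly condition, two markers and two products.
- State the detectable interaction at about 50, with its assumptions, and say that a null Hypothesis 1a is inconclusive for smaller effects. Keeping to the allowance does not itself provide power, so this statement is needed as well as the count.

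**Cost.** Some rewording and a short calculation. Fewer markers can be tested as moderators, and the stated capacity becomes less favourable. Because section 4.1 describes the modelling in the past tense, the products should be reported as specified before or after the results were seen, whichever is true.
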